The disease-free survival duration will be measured from the date of treatment to the date of documentation of disease progression or until the date of death from any cause. DFS at 6, 12 and 24 months for each patient and the series by the Kaplan-Meier method (Kaplan 1958). Also, 95% confidence intervals will be reported.

Analysis for Endpoints Related to HRQOL

We will use three instruments to measure HRQOL: the Expanded Prostate Cancer Index Composite (EPIC), the Utilization of Sexual Medications/Devices, and EQ-5D. Protocol eligible patients will be included in the HRQOL analysis only if they have provided baseline and at least one subsequent measurement. All HRQOL instruments (EPIC, the Utilization of Sexual Medications/Devices and EQ-5D) will be collected on all cases participating in the trial. The standard departments QOL instruments may also be used to report outcomes with both the International Prostate Symptom Score (IPSS) and Sexual Health Information Measurement (SHIM) obtained from chart review.

The EPIC Supplement Utilization of Sexual Medications/Devices, and EQ-5D will be collected at pretreatment (baseline) and at 6, 12 and 24 months after radiation therapy ends. Patient self-assessment of symptoms will be performed using four primary EPIC scales: urinary, bowel, hormonal and sexual symptoms. The Utilization of Sexual Medications/Devices and EQ-5D Questionnaires are found in Appendix 3.

For all primary HRQOL analyses we will estimate the degree of change from baseline to 6, 12 and 24 months as continuous variables. For this endpoint, in each domain, the actual change score will be used as the statistic and a t-test will be used to evaluate if the change is different from 0. Confidence intervals also will be computed

The primary objective in HRQOL analysis is to estimate the change from baseline to 24 months. The response will be the change of measurement from baseline to 24 months (or the last available HRQOL data point where data are missing). The one-sample t-test will be used to test the null hypothesis that response change is 0. For the regimen to maintain the overall significance level for testing three HRQOL instruments. In addition, we will describe the distributions of HRQOL data collection patterns over all collection points in each treatment arm.

Demonstrate dosimetric and biological advantage of focal SBRT versus whole-gland therapy

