10.2 Statistics

Statistical Considerations

Chi-square and cluster re-sampling analyses will be used to correlate suspicion on multiparametric magnetic resonance imaging and the incidence of cancer detected on biopsy.

The primary goal of this study is to evaluate acute and late toxicities. In addition clinical data will be collected to monitor for tumor control. Digital rectal examination (DRE) and serum prostate antigen (PSA) will be evaluated every 3 months for two years. Toxicity will be evaluated EPIC EQ D5, Sexual Medication, Device Screening Questionnaires completed by the patients or in conversation with the patient by the clinical staff, at baseline, 6, 12 and 24 months following the end of radiation therapy (+/- 14 days). Rates of acute and late side effects and adverse events will be summarized as proportions, with 95% confidence intervals.

Biochemical failure will be based on PSA values using the Phoenix definition (clinical nadir +2ng/mL). Data from all patients will be pooled. Survival rates estimated from the Kaplan-Meier curves will be estimated with 95% confidence intervals. We will also track virtual treatment plans based on standard models for treatment to the whole gland versus partial gland MRI-TPUS validated planning to report change in dosimetric parameters of the focal SBRT versus traditional whole-gland treatment plans for statistical comparison.

Either a positive DRE or rising PSA may be used as clinical indication for additional MRI surveillance. When additional MRI are available, tumor volume will be summarized by mean \pm STD and the difference between two time points (pre and post treatment) will be examined using paired T-test. Radiographic efficacy will be summarized by calculating Kaplan-Meier curves for the following: disease-free survival, time to local progression, time to distant failure. Descriptive reports of RECIST (1.1) and volumetric findings will be provided.

Acute/Late Toxicity and Quality of Life Measurements

Using multivariate analysis, we will report acute and late (>180 days post SBRT) rates of GI toxicity with dose-volume histogram. We will also report time to event analyses collected for all available HRQOL data collected.

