Temporal pattern of quality of life scores will be summarized graphically; and repeated measures analysis of variance (ANOVA) will be conducted to test for changes in scores over time. The predictive value of demographic, pathological and clinical factors on the scores will be examined by mixed models assuming missing values are missing at random.

Sample Size

Twelve patients will be evaluated in this pilot study. As a proof-of-principle study, it's not design to have the appropriate power (80%) for detecting significant difference in clinic outcomes (i.e.

toxicities, survival or QOL), but to provide some preliminary data for future studies. A sample of 12 patients, however, achieves 78% power to detect 8% difference of urinary toxicity against historical controls under whole gland therapy using a two-sided binomial test with the target significance level of 0.2. We anticipate that a minimum of twenty four patients will be screened leading to twelve patients who will be treated and evaluated on-study in this pilot study.

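### The test of change in quality-of-life scores over time is a repeated-measures ANOVA with no missing-data rule; in its standard form it would drop men whom Section 9.1 keeps

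*Combined protocol and SAP*

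**What the plan says.** Section 10.2, under the toxicity and quality-of-life heading, plans a graphical summary of the scores and then states that "repeated measures analysis of variance (ANOVA) will be conducted to test for changes in scores over time". It says nothing about men with incomplete series.

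The next sentence turns to demographic, pathological and clinical predictors of the same scores. Their effect "will be examined by mixed models assuming missing values are missing at random".

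Section 9.1 defines who enters the HRQOL analysis: eligible patients are included "only if they have provided baseline and at least one subsequent measurement". Its one gap-filling rule concerns the change from baseline to 24 months, which may use the 24-month value "or the last available HRQOL data point where data are missing". That rule belongs to a one-sample t-test and is not extended to the ANOVA.

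On size, Section 10.2 states: "Twelve patients will be evaluated in this pilot study". EPIC and EQ-5D are scheduled at baseline and at 6, 12 and 24 months (Sections 9.1 and 10.2). IPSS and SHIM are scheduled at screening and at nine follow-up visits, numbers 8 to 16 (Sections 7.2 and 7.3).

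**The concern.** Standard repeated-measures ANOVA works on a complete rectangle of patients by visits. A man who misses one scheduled form leaves the analysis, and the forms he did return go with him. The test over time could then rest on fewer men than Section 9.1 defines, and fewer than the mixed model in the adjoining sentence would use.

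Two things would be at stake in a 12-man pilot:

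- **Precision.** Each man who returns some but not all follow-up forms costs 1/12 = 8.3% of the sample.
- **Selection.** Section 7.2 takes men off study if they choose a second treatment after PSA failure, and Section 5.1 allows removal for disease progression. Later forms may therefore be missing for reasons tied to outcome, and the complete cases would lean towards men who did well.

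Some gaps are foreseeable. Section 9.0 reports IPSS and SHIM only when they happen to be collected, and Section 9.1 takes them from chart review.

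**Working it through.** The documents state no missing rate, number of completers or power for this ANOVA, so there is no figure to reproduce. The check is how many of 12 men would remain.

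**Inputs.** N = 12 (Section 10.2). T = 3 follow-up forms for EPIC and EQ-5D, T = 9 for IPSS and SHIM. Section 10.2 does not name the instruments to which the ANOVA applies; Section 7.1 classes all of them as quality-of-life scores. The missing rate m per follow-up form is an assumption, shown at 10% and 20%, with baseline taken as complete.

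**Formulas.**

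- Independent gaps: complete cases = 12 × (1 − m)^T.
- Fully clustered gaps (the same men miss every follow-up form): complete cases = 12 × (1 − m), whatever T is.
- Men kept by the Section 9.1 rule with independent gaps: 12 × (1 − m^T).

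**EPIC and EQ-5D (T = 3).**

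| m | Complete, independent | Complete, fully clustered | Kept by 9.1, independent |
|---|---|---|---|
| 10% | 12 × 0.9³ = 8.7 | 12 × 0.9 = 10.8 | 12 × (1 − 0.1³) = 11.99 |
| 20% | 12 × 0.8³ = 6.1 | 12 × 0.8 = 9.6 | 12 × (1 − 0.2³) = 11.90 |

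With independent gaps, the ANOVA uses about 11.99 − 8.75 = 3.2 fewer men than Section 9.1 admits at 10%, and 11.90 − 6.14 = 5.8 fewer at 20%. In returned follow-up forms, at 10% there are 12 × 3 × 0.9 = 32.4, of which 32.4 − 3 × 8.75 = 6.2 are unused. At 20% there are 28.8, of which 28.8 − 3 × 6.14 = 10.4 are unused.

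With fully clustered gaps, the men lost have no follow-up form at all, so Section 9.1 excludes them too and the extra loss is zero. Dropout part-way through follow-up lies between these extremes: a man who leaves after his 6- or 12-month form is kept by Section 9.1 and lost to the ANOVA.

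**IPSS and SHIM (T = 9).** Independent gaps leave 12 × 0.9⁹ = 4.6 complete cases at 10% and 12 × 0.8⁹ = 1.6 at 20%. Fully clustered gaps again leave 10.8 and 9.6.

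**The case against.** The strongest reply is that the plan never says incomplete men are dropped. It mentions neither complete cases nor software, the ANOVA label is often used loosely, and the adjoining sentence uses mixed models, so a likelihood-based fit may be intended for both. This stands as far as it goes: a reader might infer that the plan commits to listwise deletion, and the text does not support that. What it does show is a method whose standard form behaves that way, no rule to prevent it, and a mixed model named separately for a different question. If a likelihood fit is meant, the same edit would say so.

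Second, the analysis carries no decision. The co-primary endpoints in Section 9.0 are 1-year responder percentages, and the main HRQOL test in Section 9.1 is a one-sample t-test with its own missing-data rule. Section 9.1 also gives t-tests and intervals for change at 6, 12 and 24 months. Section 10.2 says the trial is not powered for QOL differences. All of this stands and limits the reach of the point.

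Third, the plan tries to limit gaps. Willingness to complete EPIC is an inclusion criterion (4.3.10), and the Appendix 3 forms accept only death or documented refusal as reasons for omission and provide for mail and telephone completion. The true rate may be low, and gaps often cluster within men, which is why the working shows both extremes.

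Fourth, a reader might add that unequally spaced visits break the ANOVA's sphericity assumption. Spacing alone does not: sphericity concerns the variances of pairwise differences, and standard corrections exist.

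Last, a mixed model at n = 12 can be fragile. An unstructured covariance over four visits needs 4 × 5 / 2 = 10 parameters. That argues for a simple structure, not for discarding returned forms.

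**Conclusion.** The point holds as a minor, cheap improvement. The missing-data handling of the test over time is unspecified, and the named method in its standard form would exclude partial completers whom Section 9.1 means to keep.

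For EPIC and EQ-5D, the range is 8.7 to 10.8 complete cases of 12 at 10% missing per form, and 6.1 to 9.6 at 20%. Compared with the Section 9.1 set, the extra loss runs from about 3.2 and 5.8 men respectively down to none. It is larger for IPSS and SHIM unless gaps are fully clustered. The rates and both patterns are assumptions.

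A reader might conclude that the trial's main quality-of-life findings are compromised. The documents do not support that: the 1-year responder endpoints and the 24-month t-test do not pass through the ANOVA. Nor is the replacement already written in the plan, since its mixed model addresses predictors and not a visit effect.

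**What to change.** Replace the ANOVA clause in Section 10.2 with a mixed model that:

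- uses the Section 9.1 HRQOL set and all available scores, with baseline as one of the outcomes;
- has visit as a categorical factor, and tests change over time as the visit effect;
- states a simple covariance in advance, for example compound symmetry or a random intercept;
- applies a Kenward-Roger or similar small-sample correction.

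The predictor analyses can then add terms to the same model.

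The cost is about one sentence, with no new data or visits. The downside is reliance on missing at random, which may be doubtful for men taken off study after PSA failure. Report the complete-case analysis as a sensitivity check and give the number of men in each. That comparison shows how far the result depends on partial completers; it does not test missing at random.

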9.0 Safety and Effectiveness Assessments

The primary goal of this pilot study is to determine if MRI with multiparametric sequences mpMRI can be used as a mapping tool for correlation with histopathology results, providing a more informed method for the delivery of focal hypofractionation treatments. Hypofractionated radiation using SBRT is a promising tool for delivery with intent to cure. The use of focal partial prostate SBRT should show lower toxicity, and will be evaluated for equivalent efficacy. A co-primary end point of the pilot study will be to show that patients maintain acceptable HRQOL status as compared to baseline. There will be two co-primary endpoints based on summary scores from the bowel and urinary domains of the EPIC questionnaire. Although HRQOL is collected at multiple time points, it has been decided that EPIC, EQ D5 and Sexual Medication/Device Screening data collected at 6, 12 and 24 months post therapy will be compared to baseline to test the primary hypothesis. The percentage of patients with change in EPIC bowel domain score (baseline to 1-year) that was worse than 5 points and a change in EPIC urinary domain score that was worse than 2 points are felt to be clinically meaningful endpoints to assess for tolerability and safety. A rate for the worse-than-5 point change in bowel score of up to 35% of patients will be considered acceptable, with a rate $\geq 55\%$ specified as unacceptable. Similarly, a rate for the worse-than-2 point change in urinary score of up to 40% will be considered acceptable, with a rate $\geq 60\%$ unacceptable. The PSA results along with serial MRI assessments will be used to test the hypothesis of equivalent disease control compared to historical data for whole gland therapy using SBRT. Standard of care quality of life assessments International Prostate Symptom Score (IPSS) and sexual health inventory for men (SHIM) scores will be acquired as part of the standard care prior to and following SBRT. When collected, this data will be collected and reported.

Analysis of the Primary Endpoints

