9.1 Safety and Efficacy Endpoints

Assessment of early clinical outcomes in focal SBRT for low risk prostate cancer patients. Twenty-four hormone naïve low to intermediate risk prostate cancer patients will be screened for PSA level, acute toxicities and quality of life (QOL) measures at baseline and twelve will be followed at longitudinal follow-up appointments.

Acute and Late GI and GU Adverse Events (AEs)

Adverse events are evaluated by the CTEP Active Version of the NCI Common Terminology Criteria for Adverse Events (CTCAE). We will record in Oncore the highest grade reported during a reporting period. The treatment-related attribution includes definitely, probably or possibly related to treatment. An acute adverse event is defined as the first occurrence of worst severity of the adverse event ≤ 30 days after the completion of RT. We will evaluate the acute radiation therapy-related adverse events. Specifically, we are interested in the percentage of acute GI and GU Grade 3+ adverse events that may occur, which is considered to be similar to the high RT dose arm of RTOG 0126 in terms of RT dose. If our partial prostate hypofractionated regimen has an acceptable percentage, then it will be deemed to have an acceptable adverse event profile. We will report the percentage for the regimen as well as the one-sided 97.5% confidence interval. For example, the number of patients in the high dose arm of RTOG 0126 Phase II reported that 1% of patients experienced Grade 3+ GI/GU acute toxicity, with no patient experiencing Grade 4 or 5 toxicities (citation) should be greater than this pilot study. A late adverse event is defined as the first occurrence of worst severity of adverse event > 180 days after RT completion. Late Grade 3+ GU/GI toxicity information will be collected and reported also.

PSA Failure

Failure occurs when the PSA is first noted to be 2 ng/mL or more than the patient's nadir value post RT completion (Phoenix, Abramowitz 2009). PSA failure at 6, 12 and 24 months following RT will be estimated for the series by the cumulative incidence method (Gray 1988). Also, confidence intervals will be reported.

Disease-Free Survival (DFS)

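### The stated 78% power for an 8% urinary-toxicity difference with 12 patients lacks a historical rate, and no test that holds level 0.2 can reach it (ceiling about 71%)

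*Combined protocol and SAP*

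**What the plan says.** Section 10.2 (Sample Size) fixes the size of the study: "Twelve patients will be evaluated in this pilot study". It then disclaims power, saying that as a proof of principle "it's not design to have the appropriate power (80%) for detecting significant difference in clinic outcomes". The next sentence partly takes this back: the sample of 12 "achieves 78% power to detect 8% difference of urinary toxicity against historical controls under whole gland therapy using a two-sided binomial test", with a target significance level of 0.2.

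Three other statements bear on the figure, though none is tied to it:

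- Section 9.0 gives the expected direction: "The use of focal partial prostate SBRT should show lower toxicity".
- Section 9.0 sets acceptability limits for the EPIC urinary score: "a rate for the worse-than-2 point change in urinary score of up to 40% will be considered acceptable", with 60% or more unacceptable.
- Section 9.1 gives one historical toxicity rate, for the high-dose arm of RTOG 0126: "1% of patients experienced Grade 3+ GI/GU acute toxicity".

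**The concern.** The power of a one-sample binomial test depends strongly on the control rate. The sentence omits that rate and its source, the direction of the difference, what counts as urinary toxicity, and the significance level actually achieved. With 12 patients the number of events takes only 13 values, so achieved level and power move in jumps and a target level alone does not define the test.

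The figure also looks too high. One patient out of 12 is 8.3 percentage points, so an 8-point difference is less than one patient. If the figure is wrong, a reader is told that such a difference is almost adequately powered, just after 80% has been named as the standard. The study says it exists to provide preliminary data for later trials, and planners of those trials are the people most likely to reuse the number.

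**Working it through.** **Inputs.** From section 10.2: n = 12, difference 8% (read as absolute; a relative 8% would be smaller and give less power), two-sided binomial test, level 0.2, stated power 78%. The historical rate p0 is not given, so all values from 0 to 1 were scanned, with p1 = p0 + 0.08 and p1 = p0 − 0.08.

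**1. Can any historical rate give 78%?** For each p0, take the rejection region R with P(X in R | p0) ≤ 0.2, where X ~ Bin(12, p0). Power is P(X in R | p1).

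| Test | p0 at the peak | Peak power |
|---|---|---|
| Equal-tail exact (0.1 per tail) | 1 − 0.9^(1/12) = 0.87% | 1 − (1 − 0.0887)^12 = 67.2% |
| Minimum-likelihood exact | 1 − 0.8^(1/12) = 1.84% | 1 − (1 − 0.0984)^12 = 71.2% |
| Neyman–Pearson, one-tailed, randomised | 1.84% | 71.2% |

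Each peak is for an increase from a rate near zero, rejecting on one or more events. There are mirror-image peaks for a reduction from about 99% and 98%. The Neyman–Pearson test is the most powerful possible at its level, so 71.2% is a ceiling for every test that holds 0.2, whichever binomial test was used.

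**2. How could 78% have arisen?** Only by exceeding the level or by using a poor approximation:

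- 10% against 2%, rejecting on 0 of 12: power 0.98^12 = 78.5%, but true level 0.90^12 = 28.2%, and the rule is one-sided.
- 3.85% against 11.85%, rejecting on one or more events: power 78%, true level 37.6%.
- A normal formula using the standard error under the alternative, 9.8% against 1.8%: SE = √(0.018 × 0.982/12) = 0.0384, and Φ(0.08/0.0384 − 1.2816) = 78.9%. Exact two-sided power there is about 0.1% or less, because even 0 of 12 is not significant.

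**3. Power for an 8-point reduction.** Historical rates are assumed. Both exact two-sided tests give the same region at each rate shown.

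| p0 → p1 | Reject if X is | Achieved level | Power |
|---|---|---|---|
| 20% → 12% | 0 or ≥5 | 0.141 | 0.216 + 0.009 = 22.5% |
| 30% → 22% | ≤1 or ≥7 | 0.124 | 0.222 + 0.007 = 22.9% |
| 40% → 32% | ≤2 or ≥8 | 0.141 | 0.208 + 0.014 = 22.2% |
| 50% → 42% | ≤3 or ≥9 | 0.146 | 20.7% |

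Between these points power follows a saw-tooth. For rates from 20% to 60% it runs from about 8% to 31%, and for no rate up to 60% does it exceed about 31%. That limit is for non-randomised two-sided tests. The corresponding ceiling for any level-0.2 test, for a reduction from a rate of 50% or less, is 57.2% (at p0 of about 12.5%).

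**4. The rates that the documents do give.** These are not labelled as the historical control.

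- 40% → 48% and 60% → 52%: 18.4% each.
- The full 20-point gap, 40% → 60%: 44.1%.
- 1% → 9%: 29.5% (equal-tail) or 67.8% (minimum-likelihood). A reduction of 8 points from 1% is impossible.

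**5. What 78% would take.** With 12 patients, a reduction of about 18 points from 20%, 23 from 30% or 26.5 from 40%. For an 8-point reduction, exact power stays at or above 78% only from about 109 patients at 20%, 146 at 30% and 167–170 at 40% (the range covers the two exact tests).

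**The case against.** The strongest reply is that the figure does no work. The sentence before it says the pilot lacks appropriate power for toxicity. Section 10.2 plans to report toxicity as proportions with 95% confidence intervals. No test of urinary toxicity against historical controls appears among the planned analyses, and no stopping or go/no-go rule uses the 78%. All of this is true. It limits the harm to one misleading planning statement, but it does not make the number correct.

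A second reply is that a target level of 0.2 leaves room for a different achieved level, and that 10% against 2% with rejection on zero events keeps the 8 points and gives 78.5%. That may be where the figure came from, though the documents do not say so. It does not rescue the sentence: the rule is one-sided where the text says two-sided, and its level is 0.28. The conclusion here is confined to tests that hold 0.2.

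A third reply is that the 40%, 60% and 1% rates were never offered as the control. That is correct. They are shown only because they are the nearest rates in the documents, and the ceiling of 71.2% does not rest on them.

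**Conclusion.** The concern holds. The power statement cannot be reproduced because its control rate is missing, and it cannot be true at any control rate for a test that holds level 0.2: the ceiling is 71.2%, reached only at rates near 0% or 100%. In the expected direction, at assumed historical rates of 20% to 40%, two-sided exact power is about 22–23%, less than a third of the stated value.

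The ceiling rests on n = 12, an absolute 8-point difference and level 0.2, all from section 10.2. The 22–23% also rests on the assumed rates. This should be fixed because it is the only power figure offered for the sample size. It does not affect the conduct of the study or its planned interval estimates.

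**What to change.** In section 10.2 (Sample Size), state the historical urinary-toxicity rate and its source, the direction, the definition of the event and the achieved significance level, then recompute exact power. The authors should check their original calculation for two possibilities, neither shown in the documents: a one-sided 10% against 2% rule, or a slip for an 18-point difference (20% against 2% gives 78.5% power at achieved level 0.141).

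If the inputs cannot be supplied, delete the sentence. If assumed rates are used, wording such as this would serve: *At assumed historical rates of 20%, 30% and 40%, 12 patients give about 22–23% power for an 8-point reduction (two-sided exact test, level 0.2); 78% power requires a reduction of about 18, 23 or 26.5 points respectively.*

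The sample of 12 can stay as a pilot size. An optional justification is precision: with 0 of 12 events, the one-sided 97.5% upper limit is 1 − 0.025^(1/12) = 26.5%, which matches the type of interval planned in section 9.1 for acute Grade 3+ events.

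Cost: one paragraph of protocol wording and no extra patients. The stated power becomes less favourable.

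### The 78% power in the sample-size paragraph belongs to a test that no analysis section makes, and with 12 men no historical rate yields it at level 0.2

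*Combined protocol and SAP*

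**What the plan says.** - **Section 10.2, Sample Size.** "Twelve patients will be evaluated in this pilot study". The paragraph first says that this proof-of-principle study was not designed for 80% power on toxicity, survival or quality of life. It then says, by way of contrast, that the sample "achieves 78% power to detect 8% difference of urinary toxicity against historical controls under whole gland therapy using a two-sided binomial test". The level given for that test is 0.2.
- **Section 10.2, Statistical Considerations.** Acute and late toxicity is called the primary goal. "Rates of acute and late side effects and adverse events will be summarized as proportions, with 95% confidence intervals".
- **Section 9.0.** "There will be two co-primary endpoints based on summary scores from the bowel and urinary domains of the EPIC questionnaire". The bowel limits are 35% (acceptable) and 55% (unacceptable). For the urinary domain, "a rate for the worse-than-2 point change in urinary score of up to 40% will be considered acceptable, with a rate $\geq 60\%$ unacceptable". No test, significance level or decision rule is attached to either pair.
- **Section 9.1, adverse events.** For acute grade 3+ GI/GU events: "We will report the percentage for the regimen as well as the one-sided 97.5% confidence interval". The text sets this beside a 1% rate in the high-dose arm of an earlier trial.
- **Section 9.1, HRQOL.** Change scores are tested against 0 with one-sample t-tests.

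**The concern.** This is the only power figure in the plan, and it concerns what section 10.2 calls the study's primary goal. A reader comes away thinking that 12 men give nearly 80% power to see an 8-point change in urinary toxicity. Two things look wrong. The test behind the figure is not among the planned analyses. The figure also looks too high for 12 binary outcomes, even at a level as lenient as 0.2. If so, a pilot that shows no difference in urinary toxicity could be taken as evidence from an almost fully powered comparison.

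**Working it through.** **Inputs.** From 10.2: n = 12, a difference of 8%, a two-sided binomial test, level 0.2. Not given: the historical rate p0 and the direction. I read 8% as percentage points, let p0 run over the whole range from 0 to 100%, and set p1 = p0 + 0.08 or p0 − 0.08.

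**Step 1: try to reproduce 78%.** For a rejection set R, the level is the sum over x in R of C(12,x)·p0^x·(1−p0)^(12−x). Power is the same sum at p1.

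- *Equal-tailed exact, at most 0.1 per tail.* The best case rejects on one or more events. This needs 1 − (1−p0)^12 ≤ 0.1, so p0 ≤ 0.87% and p1 = 8.87%. Power = 1 − 0.9113^12 = 67%.
- *Minimum-likelihood two-sided, or one-sided, exact at 0.2.* The same rule needs 1 − (1−p0)^12 ≤ 0.2, so p0 ≤ 1.84% and p1 = 9.84%. Power = 1 − 0.9016^12 = 71%.
- Both maxima are for an increase from a rate close to zero, or the mirror image close to 100%. For p0 between 20% and 60%, two-sided power is at most 29% (equal-tailed) or 38% (minimum-likelihood).
- For a reduction, which is what the study hypothesis expects, take rejection at 0/12 with a one-sided 0.2 level. This needs (1−p0)^12 ≤ 0.2, so p0 ≥ 12.55% and p1 = 4.55%. Power = 0.9545^12 = 57%.

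No exact test held at 0.2 gives 78% at any p0.

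**Step 2: where 78% could come from.** Take p0 = 10%, p1 = 2%, reject if 0/12. Power = 0.98^12 = 78.5%, but the type I error = 0.9^12 = 28%, above the stated 0.2. The normal approximation does not rescue it as a two-sided test: z at 0/12 is 0.10/√(0.10·0.90/12) = 1.15, which passes the one-sided 0.2 critical value (0.84) but not the two-sided one (1.28). Other approximate rules also come near 78% with an inflated level; for example, a one-sided z rule at 3.25% against 11.25% has 76% power and a level of 33%. The documents do not say which calculation was used.

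**Step 3: compare the powered test with the planned analyses.**

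| Place | Endpoint | Reference | Method |
|---|---|---|---|
| 10.2 Sample Size | urinary toxicity | historical controls, rate not given | two-sided binomial, 0.2 |
| 9.0 | EPIC bowel and urinary declines | 35%/55% and 40%/60% | none stated |
| 9.1 adverse events | acute grade 3+ GI/GU | 1% in an earlier trial | percentage, one-sided 97.5% interval |
| 9.1 HRQOL | change scores | 0 | one-sample t-test |
| 10.2 Statistical Considerations | side-effect and adverse-event rates | none | proportions, 95% intervals |

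No later row is the test in the first row.

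**Step 4: what 12 men do give.** Exact (Clopper–Pearson) 95% intervals:

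- 0/12: 0 to 1 − 0.025^(1/12), that is 0–26.5%
- 3/12: 5–57%
- 6/12: 21–79%

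**Step 5: the EPIC limits, as illustration only.** Take each unacceptable rate as the null, 12 evaluable men, and power at the acceptable rate.

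| Domain | One-sided 0.2 | One-sided 0.025 |
|---|---|---|
| Bowel, 55% against 35% | ≤4/12: error 11%, power 58% | ≤2/12: power 15% |
| Urinary, 60% against 40% | ≤5/12: error 16%, power 67% | ≤3/12: power 23% |

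**The case against.** The best defence is the paragraph's own disclaimer. The study calls itself a pilot, says that it is not powered for toxicity, survival or quality of life, and ties no decision or stopping rule to the 78%. That stands, and it limits the consequence: no confirmatory claim fails. It does not cure the figure, because the next sentence offers 78% as what the sample achieves.

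A second defence is that the mismatch is smaller than it looks. Section 10.2 says that toxicity will be evaluated with the questionnaires, so urinary toxicity might mean the EPIC urinary proportion, and section 9.1 does refer to a historical rate. Both observations are fair. But the EPIC limits are fixed rates 20 points apart and not historical controls, while the 9.1 comparison concerns combined GI/GU grade 3+ events with a one-sided 97.5% interval. Neither is a test of an 8-point urinary difference at 0.2.

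Two stronger readings are tempting and are not supported. A reader might infer that the co-primary endpoints have far less than 78% power, or about 39% if both must be met and are independent (0.665 × 0.583). Section 9.0 states no level, cut-off or both-must-pass rule, and the Step 5 figures are for 20-point differences, so they cannot be ranked against a power for 8 points. At one-sided 0.2 the gap would in any case be moderate. A reader might also infer that the plan makes no historical comparison at all; section 9.1 makes one.

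**Conclusion.** The point holds in this form: the 78% is attached to a test that the plan does not carry out, its key inputs are missing, and it cannot be obtained with 12 men at a true level of 0.2 or less. The ceiling for an 8-point difference is 67% equal-tailed, or 71% with the minimum-likelihood or one-sided version, and it is reached only at historical rates of about 1–2% (or their mirror image). This rests on an exact one-sample binomial test, all 12 men evaluable, and 8% read as percentage points. It does not depend on guessing the historical rate, since all rates were scanned in both directions. It is a misleading statement that should be corrected, and not a reason to call the pilot unsound. Nothing here establishes the power of the EPIC co-primaries, because the plan gives them no test.

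**What to change.** In section 10.2, Sample Size:

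- Delete the 78% sentence and keep the statement that the pilot is not powered for toxicity, survival or quality of life.
- Put precision in its place, for example: *With 12 evaluable men, exact 95% confidence intervals would be 0–26.5% for 0 events, 5–57% for 3 and 21–79% for 6.*
- State that the EPIC limits in section 9.0 carry no formal test or level. If the investigators want a pass/fail rule, they choose the cut-offs, and whether both domains must pass, and report the error rates of that rule. The Step 5 figures may help but are not a proposed rule.
- In section 9.1, describe the comparison with the earlier trial's 1% acute grade 3+ rate as descriptive, reported with its one-sided 97.5% interval. Even 0/12 leaves an upper limit of 26.5%.

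If the sponsor prefers to keep a power statement, it needs the historical rate and its source, the direction, grade, time point, exact test and actual type I error, and the same test must appear in the analysis section.

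The cost is one paragraph in 10.2 and a clarifying sentence in each of 9.0 and 9.1. No patients, visits or data are added. The downside is that the stated power becomes less favourable.
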